6. GENERAL ANALYSIS DEFINITIONS

6.1 **TREATMENT(S)**

The following treatment periods based on actual start and stop dates/times of randomised study drug administration are defined:

- Screening: date of informed consent (time "0:00:00") to date of randomisation (time "0:01:00")
- Post-randomisation: date of randomisation (time "0:01:00") to time-point of first intake (date and time, "0:02:00" if time is missing) of randomised study drug.
- On-treatment: first intake (date and time)/date restarted of randomised study drug to date stopped/last intake (date and time) of randomised study drug. The residual effect period (REP) of 6 days will be added to this period.
- Off-treatment: date randomised study drug stopped + REP to date randomised study drug restarted
- Post-treatment: last intake (date/time) of randomised study drug + REP until date of trial completion. This is the date given on the termination page (trial completion page) of the eCRF. If date of trial completion is before last intake + REP, REP will be cut accordingly.
- Post-study: day after date of trial completion to database lock (DBL) + 1 day (time "0:00:00").

The REP is the time period after the last administration of trial medication when measurable drug levels or pharmacodynamic effects are still likely to be present. Events occurring in the REP are handled as occurring on-treatment. Data from the post-study period will only be listed.

For the analysis two observation periods are defined:

- Full observation period: from date of randomisation until the end of the trial, including all observed time on and off trial medication until the last known alive date (or date of death) This observation period will be used for the efficacy analysis.
- On-treatment: from date of first intake of trial medication until discontinuation of trial medication + REP

This observation period will be used for the safety analysis.

Despite the trial being open label, all activities conducted by the trial team will be performed in a blinded manner (as much as possible) until DBL. For example, data tabulations and listings will be presented using dummy treatment group information instead of actual treatment group allocations. The planned data review will be handled by the DMC in an unblinded manner (refer to the DMC SAP for more information).

6.2 IMPORTANT PROTOCOL VIOLATIONS

The following table defines the different categories of important protocol violations (IPVs). The final column describes which IPVs will be used to exclude patients from the different patient analysis sets. In this study, patients are either excluded from "All" analysis sets, the

 TSAP for BI Trial No: 1160.248
 Page 14 of 30

 Proprietary confidential information © 2018 Boehringer Ingelheim International GmbH or one or more of its affiliated companies

PPS, the FAS or "None" of the analysis sets. Refer to Section 6.3 for more details. IPVs will be identified by the trial team prior to DBL in a blinded manner [4].

Important protocol violations Table 6.2: 1

Cat	egory /	Description	Requirements	Excluded
Code				from
Α		Entrance criteria not met		
	A1.1	Male or female patients. Women of	Inclusion criterion 2 not met as	None
		childbearing potential must be ready and	specified in the protocol.	
		able to use highly effective methods of		
		birth control		
	A1.2	Age \geq 18 years and < 79 years at Visit 1	Inclusion criterion 3 not met as	PPS
			specified in the protocol.	
	A1.3	Confirmed diagnosis of CVT, with or	Inclusion criterion 4 not met as	PPS
		without ICH	specified in the protocol.	
	A1.4	Patient has achieved clinical stability	Inclusion criterion 5 not met as	PPS
		after having received standard acute	specified in the protocol.	
		CVT treatment as required, including		
		anticoagulation therapy for 5-15 days		
		which has been administered until		
	415	randomisation.		DDC
	A1.5	Eligibility for treatment with an oral	Inclusion criterion 6 not met as	PPS
		anticoaguiant for their C v I, based on	specified in the protocol.	
		investigator judginent. Based on fisk		
		should be a candidate		
		for at least 24 weeks of oral		
		anticoagulation		
	A1.6	Availability for external review of the	Inclusion criterion 7 not met as	None
	11110	imaging that was used to diagnose the	specified in the protocol.	i tone
		CVT	-F	
	A2.1	Inability to swallow trial medications	Exclusion criterion 1 met as specified in	PPS
			the protocol	
	A2.2	CVT associated with central nervous	Exclusion criterion 2 met as specified in	PPS
		system infection	the protocol	
	A2.3	CVT due to head trauma	Exclusion criterion 3 met as specified in	PPS
			the protocol	
	A2.4	Planned for surgical treatment for CVT	Exclusion criterion 4 met as specified in	PPS
			the protocol	
	A2.5	Patient with conditions associated with	Exclusion criterion 5 met as specified in	PPS
		increased risk of bleeding	the protocol	
	A2.6	Life-threatening or major bleeding (per	Exclusion criterion 6 met as specified in	PPS
		ISTH criteria) other than intracranial	the protocol	
		bleeding due to inclusion CVT, during		
		the 6 months prior to randomisation or		
		while on anticoagulants during the acute		
	127	pnase of UV I		DDC
	A2./	History of symptomatic non-traumatic	Exclusion criterion / met as specified in	PPS
		homombagia strake within 6 months	the protocol	
		prior to Visit 1)		

 TSAP for BI Trial No: 1160.248
 Page 15 of 30

 Proprietary confidential information © 2018 Boehringer Ingelheim International GmbH or one or more of its affiliated companies

Table 6.2: 1 Important protocol violations (continued)

Cate	egory /	Description	Requirements	Excluded
Code		1	1	from
	A2.8	Severe renal impairment defined as CrCl (calculated by Cockcroft-Gault equation) <30mL/min at screening, or if the Investigator expects CrCl is likely to drop below 30mL/min during the course of the trial	Exclusion criterion 8 met as specified in the protocol	PPS
	A2.9	Patients who are taking any of the drugs listed as restricted in CTP section 4.2.2.1 while on active treatment with study drug	Exclusion criterion 9 met as specified in the protocol	PPS
	A2.10	Patients receiving treatment with warfarin, dabigatran etexilate or other antithrombotic regimen (i.e. anticoagulants or anti-platelet medication) for an indication other than CVT and requiring continuation of that treatment for the original diagnosis without change in the regimen	Exclusion criterion 10 met as specified in the protocol	None
	A2.11	Patients with prosthetic heart valves	Exclusion criterion 11 met as specified in the protocol	PPS
	A2.12	Known hypersensitivity to dabigatran etexilate or warfarin or to any of the excipients of either product	Exclusion criterion 12 met as specified in the protocol	None
	A2.13	Any current or recent malignancy (≤ 6 months prior to Visit 1) unless the malignancy was a basal cell carcinoma that was completely removed	Exclusion criterion 13 met as specified in the protocol	PPS
	A2.14	Concomitant disease that increases the risk of an adverse reaction to trial interventions or with life expectancy < 6 months (for any reason) per Investigator judgment	Exclusion criterion 14 met as specified in the protocol	PPS
	A2.15	Pre-menopausal women (last menstruation ≤ 1 year prior to Visit 1) who are pregnant, nursing, or who plan to become pregnant while in the trial.	Exclusion criterion 15 met as specified in the protocol	None
	A2.16	Patients who have participated in another trial with an investigational drug or device within the past 14 days preceding Visit 1 or who currently are participating in another trial. Patients who are still experiencing a clinical effect from an investigational drug or device.	Exclusion criterion 16 met as specified in the protocol	None
	A2.17	Patients considered unreliable by the Investigator concerning the requirements for follow-up during the trial or at the end of the trial.	Exclusion criterion 17 met as specified in the protocol	None
	A2.18	Any condition the Investigator believes would not allow safe participation in the trial.	Exclusion criterion 18 met as specified in the protocol	None
	A2.19	Active liver disease	Exclusion criterion 19 met as specified in the protocol	None

 TSAP for BI Trial No: 1160.248
 Page 16 of 30

 Proprietary confidential information © 2018 Boehringer Ingelheim International GmbH or one or more of its affiliated companies

Table 6.2: 1 Important protocol violations (continued)

Category /		Description	Requirements	Excluded
Code				from
	A2.20	Previous randomisation in this trial	us randomisation in this trial Exclusion criterion 20 met as specified	
-			in the protocol	
B	D1	Informed consent		. 11
	BI	Informed consent not available/not done	Inclusion criterion 1 not met as	All
	D1		specified in the protocol.	Neue
	B 2	Informed consent too fate	date	None
C		Trial medication and randomisation		
C	C1	Incorrect trial medication taken	Medication kit assigned not matching	PPS
	01	incorrect that incurcation taken	treatment patient was randomised to	115
			(cross-treatment) and/or not matching	
			IRT assignment	
	C2	Randomisation order not followed, e.g.	Cases will be identified from IRT	PPS
		forced randomization, misstratification	reports and read in via the manual PV	
			spreadsheet	
	C3	Non-Compliance	Compliance <80% or >120% over the	PPS
			course of the study for dabigatran	
			patients, or time in therapeutic target	
			range for warfarin patients <45%. See	
			Section 7.3 for details on compliance	
			Non compliance caused by temporary	
			interruption of the treatment due to a	
			procedure or a drop in CrCl to less than	
			30 mL/min should not be classified as a	
			protocol violation.	
D		Concomitant medication		
	D1	Prohibited medication use	See CTP section 4.2.2.1	PPS
			Those treatments should not be taken	
			during the active treatment phase of the	
			trial:	
			- Fibrinolytic agents (refer to	
			CIP section 4.2.1.5 for	
			CPUb/ULa antagonista (a g	
			- GPH0/IIIa antagonists (e.g.	
			- Rivaroxahan aniyahan and	
			edoxaban, or other oral	
			anticoagulants (e.g. VKAs)	
			- Treatment with systemic	
			ketoconazole, itraconazole,	
			posaconazole, cyclosporine,	
			tacrolimus and dronedarone,	
			and rifampicin, carbamazepine,	
			phenytoin and St. John's Wort	
			Medications will be identified through	
			medical review and details will be	
			provided in the technical TSAP.	

Table 6.2: 1	Important protocol	l violations	(continued)
--------------	--------------------	--------------	-------------

Cate	egory /	Description	Requirements	Excluded
Cod	le	1	•	from
G		Trial Specific Protocol Violations		
	G1	Patient randomized to dabigatran		PPS
		etexilate not withdrawn from trial		
		treatment if CrCl drops to <30mL/min at		
		two different occasions during the trial or		
		drops to <30mL/min and does not		
		recover to above 30 within 7 days		
	G2	Creatinine clearance not measured / not		PPS
		reviewed prior to start of treatment		
	G3	Woman of child bearing potential and		None
		pregnancy test not confirmed to be		
		negative prior to start of trial treatment		
	G4	Woman become pregnant during the trial		None
	G5	Patient on VKA prior to randomization,		PPS
		randomized to dabigatran etexilate and		
		treated although INR not confirmed to be		
		<2.0		
	G6	Patient on VKA prior to randomization,		PPS
		randomized to warfarin and treated		
		although INR not confirmed to be <3.0		
	G7	Patient randomized to warfarin and		PPS
		treated and UFH / LMWH stopped		
		although INR not confirmed to be ≥ 2.0		

The following IPV are programmed automatically: all from A and B, C3, D1, G1, G3-G7.

The remaining IPV are manual IPVs and need to be identified at a site level on the manual PV log.

The frequency of patients with IPVs will be presented. Those which lead to a patient being excluded from the PPS will be presented separately to those which do not.

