A patient should also be permanently discontinued from trial medication if CrCl drops <30mL/min on two different occasions during the trial. During period of interruption, a patient can be treated per standard of care according to Investigator's discretion.
- The patient can no longer be treated with trial medication for other medical reasons (such as surgery, AEs, other diseases).
- The patient has repeatedly shown to be non-compliant with important trial procedures and, in the opinion of both, the investigator and sponsor representative, is not willing or able to stick to the trial requirements in the future.

Guidelines for transitioning to non-study antithrombotic medications are provided in Appendix [10.2](#).

Given the patient's agreement, the patient will undergo the procedures for early treatment discontinuation and follow up as outlined in the [Flow Chart](#) and Section [6.2.3](#).

For all patients the reason for withdrawal (e.g. AEs) must be recorded in the Case Report Form (CRF). These data will be included in the trial database and reported.

If a trial patient becomes pregnant, the trial medication will be discontinued permanently. All end of treatment (EOT) procedures should be performed and the patient should be followed in the trial as outlined in the Flow Chart and below for patients who discontinue trial medication early.

In addition the patient will be followed up until birth or otherwise termination of the pregnancy. See also Section [5.3.7](#).

The data of the patient until last patient last visit (for the total trial) will be collected and reported in the clinical trial report. Any events thereafter will be reported in the BI drug safety database only.

Patients who discontinue trial treatment before completing 24 weeks of treatment will be followed-up for the collection of further data on \_\_\_\_\_, MBEs, VTEs, any other AEs and post-study anti-coagulation therapy (until 25 weeks after the date of randomisation), unless they withdraw their consent for any further participation. Data will be collected during a contact at 25 weeks after randomisation and from existing medical records. Every effort should be made to obtain this information. Patients who discontinue trial medication and who do not agree to be contacted themselves should be asked if they agree to another person being contacted to obtain this information. Contact details of that person should then be obtained.

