### **DVT, PE or splanchnic vein thrombosis**

An event of DVT, PE or splanchnic vein thrombosis occurring during the trial treatment period should be treated according to local clinical practice. Trial treatment should be interrupted if the patient is being treated with other anticoagulation therapy or with other medication that is restricted per Section [4.2.2.1](#). The decision for restarting trial treatment is at the discretion of the Investigator.

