## **4.2.2      Restrictions**

### **4.2.2.1      Restrictions regarding concomitant treatment**

The following treatments should not be taken during the active treatment phase of the trial:

- Fibrinolytic agents (see Section [4.2.1.5](#) for exceptions)
- GPIIb/IIIa antagonists (e.g. abciximab, tirofiban)
- Rivaroxaban, apixaban and edoxaban, or other oral anticoagulants (e.g. VKAs)
- Treatment with systemic ketoconazole, itraconazole, posaconazole, cyclosporine, tacrolimus and dronedarone, and rifampicin, carbamazepine, phenytoin and St. John's Wort
- Any type of dual antiplatelet therapy

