### **OPTION 1: STARTING VKA PRIOR TO DABIGATRAN ETEXILATE DISCONTINUATION**

Start VKA at the EOT Visit and continue on dabigatran etexilate for 2-3 days after the EOT Visit.

- In patients with CrCl >50mL/min who discontinue dabigatran etexilate but still require anticoagulation, dabigatran etexilate should be continued for three days together with VKA.
- For patients with moderate renal dysfunction (CrCl  $\geq$ 30 to <50mL/min), as measured in the visit before EOT, dabigatran can be stopped after two days of concomitant VKA.

Many physicians will want to see VKA naïve patients before starting VKA. There is no special need to measure the INR before starting a VKA. If the INR is checked on the day of the EOT visit, Investigators should recognise that the presence of dabigatran etexilate could elevate the INR. Because dabigatran etexilate can increase the INR, the INR will better reflect warfarin's effect only after dabigatran etexilate has been stopped for at least 24 hours.

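### As written, protocol violation D1 can drop patients from the per-protocol set for oral anticoagulant use the protocol itself foresees, including treatment of a primary-endpoint VTE

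*SAP*

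**What the plan says.** **The exclusion rule.** SAP 6.2, Table 6.2: 1, code D1 is headed "Prohibited medication use" and leads to exclusion from the PPS. It repeats most of the list in Protocol 4.2.2.1, which includes "Rivaroxaban, apixaban and edoxaban, or other oral anticoagulants (e.g. VKAs", and applies to the active treatment phase. Neither document defines that phase. The only exception D1 points to is for fibrinolytic agents (Protocol 4.2.1.5).

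**How it is applied.** SAP 6.2 states: "The following IPV are programmed automatically: all from A and B, C3, D1, G1, G3-G7". The D1 row also says "Medications will be identified through" medical review, with details left to a technical TSAP. In general, "IPVs will be identified by the trial team prior to DBL in a blinded manner".

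**What the protocol foresees.**
- Protocol 4.2.1.6, new DVT, PE or splanchnic vein thrombosis: treatment follows local practice, and "Trial treatment should be interrupted if the patient is being treated with other anticoagulation therapy". The CVT paragraph is similar and mentions restricted medication explicitly. Restart is left to the investigator.
- Protocol 3.3.4.1, CrCl below 30 mL/min in the dabigatran arm: "During period of interruption, a patient can be treated per standard of care according to Investigator's discretion".
- Protocol Appendix 10.2, Option 1: "Start VKA at the EOT Visit and continue on dabigatran etexilate for 2-3 days after the EOT Visit".

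**Use of the PPS.** SAP Table 6.3: 1 lists it for a secondary analysis of the primary endpoint. SAP 6.3 allows that analysis to be skipped if fewer than 10% of the treated set are excluded.

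**The concern.** A per-protocol set should leave out patients who departed from the protocol. D1 has no exception for oral anticoagulants in three situations where the protocol requires, allows or leaves room for them. In the VTE situation there is a second problem: the anticoagulant is given because the primary endpoint has occurred. Excluding the patient is then selection on the outcome. Everyone with a confirmed VTE who leaves by this route takes an event with them, so the PPS event rate can only look better as a result.

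Blinded identification of violations does not prevent this. It hides the treatment arm, not the reason the anticoagulant was given.

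At stake is the PPS result as a check on the primary analysis, in a trial that relies on the two arms showing comparable event frequencies (Protocol 7.7). D1 flags also count towards the 10% threshold that decides whether the PPS analysis is run.

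**Working it through.** **1. Is such use inside the D1 period?** The period is undefined, so the candidate readings have to be compared.

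| Situation | First to last intake, interruptions removed | SAP 6.1 on-treatment period (intake plus 6 days) | Phase ends at the EOT visit, interruptions included |
|---|---|---|---|
| Oral anticoagulant for a VTE, trial drug interrupted | Not flagged | Flagged if taken within 6 days of stopping | Flagged |
| Oral anticoagulant in a CrCl interruption | Not flagged | Flagged if taken within 6 days of stopping | Flagged |
| VKA with dabigatran, Option 1 | Flagged | Flagged | Flagged only if the EOT visit day counts |

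No column clears all three rows beyond doubt. The middle column matters most: it is the only on-treatment period the SAP defines, and SAP 7.2 uses it to decide which therapies are concomitant.

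**2. Comparison with C3.** In the same table, C3 (non-compliance) exempts temporary interruptions for a procedure or a drop in CrCl. D1 has no matching text, so the same CrCl interruption can be excused under C3 and flagged under D1.

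**3. The plan's own sample size (Protocol 7.7).** 120 × (1 − 0.10) = 108 evaluable, and 60 × 0.90 = 54 per arm. Both reproduce.

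**4. Expected events.** Protocol 7.7 assumes a 2 to 3% event rate.
- Total: 0.02 × 120 = 2.4 and 0.03 × 120 = 3.6.
- Per arm: 0.02 × 60 = 1.2 and 0.03 × 60 = 1.8.
- One lost event as a share of the expected total: 1/3.6 = 28% to 1/2.4 = 42%.

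**5. Effect on one arm.** Suppose an arm has two events and one is a VTE whose treatment triggers D1. Exact (Clopper-Pearson) 95% intervals:

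| Patients in arm | All events kept | One event patient excluded |
|---|---|---|
| 54 evaluable | 2/54 = 3.7% (0.5 to 12.7%) | 1/53 = 1.9% (0.05 to 10.1%) |
| 60 randomised | 2/60 = 3.3% (0.4 to 11.5%) | 1/59 = 1.7% (0.04 to 9.1%) |

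The point estimate roughly halves. The intervals overlap almost entirely.

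**6. The 10% threshold.** If all 120 are treated, 0.10 × 120 = 12. The documents do not say how many dabigatran patients will switch by Option 1. Assumed shares of 10%, 20%, 30% and 50% of 60 give 6, 12, 18 and 30 patients. If Option 1 use is flagged, a 20% share alone reaches the threshold. These shares are assumptions, not forecasts.

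**The case against.** **Exclusion is not established.** D1 also calls for medical review and defers its details to a technical TSAP that is not among these documents. Protocol 4.3 leaves decisions on evaluability to a blinded meeting before database lock. A reader might infer that every patient in the three situations will be removed. The documents do not support that. What remains is that the SAP gives no rule on timing or reason for use, and that it places D1 among the programmed violations rather than the manual ones.

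**A narrower period is plausible.** Exclusion criterion 9 and code A2.9 apply the same drug list to time on active treatment with study drug. Protocol 4.2.1.6 has trial drug interrupted while the other therapy is given. On that reading, use during an interruption is not flagged. This is a fair point, but the SAP does not adopt that reading, and its defined on-treatment period adds 6 days.

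**Option 1 may fall after treatment.** Protocol 4.1.4.1 and the Flow Chart end regular trial medication at the EOT visit. However, Protocol 6.2.3 describes the overlap as continued trial medication, so any rule based on actual intake would flag it.

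**One-arm thinning.** A reader might infer that switching removes dabigatran patients only. That holds only if the period runs from first to last intake. If the 6 extra days count, warfarin patients who start a non-study oral anticoagulant soon after EOT are also flagged. If the period ends before the switch, nobody is.

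**Route.** Protocol 4.2.1.6 does not specify oral agents, and general bridging (Protocol 4.2, Appendix 10.1.3) is parenteral and not on the D1 list. The point is limited to oral use.

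**Impact.** The trial tests no hypothesis, and the PPS analysis is secondary and conditional. VTE as an endpoint in its own right is analysed on the full analysis set. All of this stands and limits the weight of the point.

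**Conclusion.** The point holds as a gap in the written rule. D1 can exclude patients for oral anticoagulant use the protocol foresees, and in the VTE situation the exclusion can follow from the primary-endpoint event. With 2.4 to 3.6 events expected, one such exclusion would take out 28 to 42% of the expected total and could halve an arm's PPS rate. That size rests on the protocol's assumed event rate and on at least one VTE being treated with an oral anticoagulant inside the D1 period. The numbers excluded through Option 1, and whether one or both arms are affected, cannot be determined from the documents.

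A reader might go further and conclude that the trial's main result is biased. It is not affected: the primary analysis uses all randomised patients over the full observation period, whatever else they took. The change is worth making before database lock but is not critical to the primary analysis.

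**What to change.** **In the D1 row of SAP Table 6.2: 1:**
1. Define the window as the time from first to last intake of trial drug, leaving out documented interruptions and the 6-day residual effect period.
2. State that anticoagulant or antithrombotic treatment given for an adjudicated primary-endpoint event, and started on or after its onset, does not lead to PPS exclusion.
3. State the same for anticoagulants given as part of the Appendix 10.2 switch. This must be explicit, because under Option 1 the last intake falls after the EOT visit and the overlap lies inside the window.
4. Keep every other restricted drug as a violation whenever it is taken in the window, including after an event. A blanket exemption for anything started after an event would be wider than the problem.

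**Reconcile:**
- In SAP 6.2, automatic programming with medical review: say what the program flags, what the review decides and by which rule.
- Protocol 4.2.2.1 with Appendix 10.2, on VKA taken together with trial dabigatran. This review takes no position on which clinical instruction should stand.

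**Cost.** One table row, a date condition in the violation program, and a clarification in the protocol. No new data are needed: the protocol already has concomitant therapy start dates, outcome event onset dates, interruptions and last intake recorded. Some dates may be incomplete and imputed under SAP 6.6, so borderline cases should be listed.
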